2.1. Overall Study Design and Plan

This is a randomized, double-blind, placebo-controlled, parallel group, multi-site study in non-hospitalized adult subjects who test positive for SARS-CoV-2 and have COVID-19 symptom onset within 5 days of randomization and who are not at high risk for progression to severe COVID-19. Subjects can be vaccinated or unvaccinated for COVID-19. Subjects with prior COVID-19 infection <90 days before enrollment and/or who received a COVID-19 vaccine dose <90 days before enrollment are excluded from trial participation.

[figure not shown]
Subjects will be randomized in a 1:1:1 ratio to receive either EDP 235 [REDACTED], EDP 235 [REDACTED], or placebo orally once daily for 5 days. Randomization will be stratified by age (≤ 50 years or 51 to 64 years) and by the duration of COVID-19 symptoms (≤ 3 days or >3 days and ≤ 5 days).

The study includes 4 periods:

- Screening period will occur from Day -1 to Day 1. Screening should be completed as soon as possible, and the subject will be randomized within 24 hours of signing the ICF. A subject will be considered enrolled at the time of randomization.
- Treatment period will begin with the first dose of study treatment on Day 1 and will conclude with the end-of-treatment (EOT) visit on Day 5.
- Follow-up period will begin following the last dose of study treatment and will conclude at the end of follow-up (EOFU) visit on Day 33 (28 days after the last dose of study treatment).
- Long-term follow-up period (LTFU) will begin at Day 34 and concludes at the end-of-study (EOS) visit at Week 24.

An overview of the study design is shown in **Figure 1**. Study site visits and assessments are detailed in the Schedule of Study Procedures ([Appendix 14.1](#)).

Figure 1: Study Design

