3.4.3. Intent-to-Treat-c (ITT-c)

The Intent-to-Treat (ITT-c) Population includes all subjects in the SAF Population with their SARS-CoV-2 status confirmed by central RT-PCR viral load at baseline \geq lower limit of quantification (LLOQ) and with at least one post-baseline primary efficacy measurement. Subjects will be analyzed as randomized.

The reasons for exclusion from the ITT-c population will be summarized by treatment group using the Safety population.

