5.3. Baseline Disease Characteristics

The following baseline disease characteristics will be presented by treatment group and overall and stratified by age group and duration of baseline COVID-19 symptoms (≤ 3 days or > 3 days and ≤ 5 days) for all subjects in the SAF, ITT-c and PP populations. Additionally, baseline disease characteristics will be listed for all subjects in the SAF population.

- SARS-CoV-2 RNA viral load
- Infectious SARS-CoV-2 viral load
- SARS-CoV-2 RNAemia
- SARS-CoV-2 serostatus
- Respiratory pathogen test
- SARS-CoV-2 variant
- COVID-19 symptom diary total score

- COVID-19 symptom diary severity

SARS-CoV-2 RNA viral load, Infectious SARS-CoV-2 viral load and SARS-CoV-2 RNAemia will also be summarized as positive, negative and missing where either a numeric or “POS” result is considered positive and TND is considered negative.

Baseline SARS-CoV-2 serostatus will be based on Day 1 SARS-CoV-2 anti-nucleocapsid and anti-spike IgG, and IgM antibodies. If at least one qualitative result is positive or IgM > 1.0, the serostatus will be considered positive. In order to be considered negative, all four results must be non-missing, all qualitative results must be negative and IgM equal to “<1.0”.

A description of how symptoms are scored from the COVID-19 Symptom Diary is in [Appendix 14.2](#). The total symptom score and the following severity categories will be presented:

- Only mild symptoms at Day 1
- 1 moderate and no severe symptoms
- 2 or more moderate symptoms and no severe symptoms
- 1 or more severe symptom(s) and no moderate symptoms
- 1 or more severe symptom(s) and 1 or more moderate symptom(s)

6. Treatments and Medications

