7.4. Electrocardiogram

All Electrocardiogram (ECG) results will be summarized by treatment group and visit in the Safety population and a listing will be presented of all results with abnormalities flagged.

8. Efficacy Analysis

Unless otherwise specified, efficacy analyses will be performed using ITT-c population and the following methods will be implemented:

For time to event endpoints time and date will be used and 24 hours will be considered as a day. Descriptive statistics using the Kaplan-Meier method will include the median, 25th percentile, and 95% CIs (log-negative-log transformation). Additionally, the cumulative event rate (SE) will be summarized by treatment group and presented graphically over time. For between group comparisons, Cox Proportional Hazards models (tie handling will be addressed first using the exact method then with Efron's method if the exact method does not converge) will include treatment group, randomization stratification factors of age (≤ 50 years or 51 to 64 years) and duration of COVID-19 symptoms (≤ 3 days or >3 days and ≤ 5 days), and the baseline value of the endpoint. The hazard ratios with associated 95% CIs (Wald) and p-values (analysis of maximum likelihood estimates) comparing EDP 235 [REDACTED] versus Placebo, and EDP 235 [REDACTED] versus Placebo will be reported. Model assumptions will be checked via a log-negative-log plot and/or Schoenfeld residuals as appropriate. Subjects who do not achieve the specified endpoint will be censored with time imputed as treatment start time as follows:

COVID-19 diary:

- Subjects who have not been followed through the Day 33 visit (discontinuation from study or incomplete follow-up at the time of analysis) or completed Day 33 diary will be censored at Day 33.

Other time to event endpoints:

- Subjects who discontinued from the study will be censored at Day 33.
- Subjects who have completed the Day 33 visit will be censored at Day 33 Visit Date.

For treatment comparisons of change from baseline endpoints, analysis of covariance (ANCOVA) models will include treatment group, randomization stratification factors of age (≤ 50 years or 51 to 64 years) and duration of COVID-19 symptoms (≤ 3 days or >3 days and ≤ 5 days) and baseline value of the endpoint as the covariate. The least-squares means, SE, and 95% CIs will be presented for individual groups and the difference between groups. The p-value for

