The proportion of subjects with positive SARS-CoV-2 serostatus will be defined the same as baseline SARS-CoV-2 serostatus ([Section 5.3](#)) and summarized for each treatment group and will be analyzed using the same CMH methods as described for the primary endpoint in [Section 8](#).

[REDACTED]

[REDACTED]

[REDACTED]

[REDACTED]

[REDACTED]

[REDACTED]

[REDACTED]

[REDACTED]

[REDACTED]

[REDACTED]

[REDACTED]

collection. Time and date of collection will be recorded on the Plasma PK Sample Collection eCRF.

For subjects included in the PK population, the concentration data for EDP 235 will be summarized by study day, collection time relative to dose and by treatment group. Only Day 1 postdose, and Day 3 and Day 5 predose concentration data will be summarized for the PK population. Concentrations <LLOQ will be treated as zero for the computation of descriptive statistics. If more than 50% of subjects have concentration values <LLOQ, descriptive statistics will not be presented except for maximum and BQL (below quantification limit) will be displayed for mean and minimum, respectively. The number of observations, arithmetic mean, standard deviation (SD), % coefficient of variation (%CV), median, minimum, maximum, geometric mean, and %CV of the geometric mean (%GCV) will be summarized.

Mean (+/-standard error) and individual PK concentration over Study Day (Days 1, 3, and 5) by treatment group will be plotted on linear and semi-log scale.

Individual concentration data will be presented in listings.

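### The Day 33 serostatus endpoint mixes antibodies from vaccination or older infection with the response to the current infection, which dilutes any treatment contrast in proportion to Day 1 seropositivity

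*SAP*

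**What the plan says.** Section 8.3.7 sets the Day 33 endpoint by reference to the baseline rule: "The proportion of subjects with positive SARS-CoV-2 serostatus will be defined the same as baseline SARS-CoV-2 serostatus". It sends the comparison between arms to the CMH method of Section 8.

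Section 5.3 gives the baseline rule. The inputs are: "Baseline SARS-CoV-2 serostatus will be based on Day 1 SARS-CoV-2 anti-nucleocapsid and anti-spike IgG, and IgM antibodies". The threshold is: "If at least one qualitative result is positive or IgM > 1.0, the serostatus will be considered positive". A negative status needs every result present and negative.

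Section 2.1 describes who is enrolled: "Subjects can be vaccinated or unvaccinated for COVID-19". It also sets the only visible limit on earlier immunity: "Subjects with prior COVID-19 infection <90 days before enrollment and/or who received a COVID-19 vaccine dose <90 days before enrollment are excluded from trial participation". Vaccination or infection 90 or more days before enrollment is therefore allowed.

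Section 8 sets the default analysis set: "Unless otherwise specified, efficacy analyses will be performed using ITT-c population". Section 3.4.3 requires members of that set to have "SARS-CoV-2 status confirmed by central RT-PCR viral load at baseline" at or above the quantification limit. The CMH test in Section 8 is stratified by the two randomization factors, age and symptom duration. The visible text of Section 8.3.7 neither restricts the analysis to participants who were seronegative on Day 1 nor adjusts for baseline serostatus or vaccination, and it does not separate the antibodies.

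**The concern.** A rule suited to describing immunity at entry is reused as an outcome after treatment. A participant who arrives with anti-spike IgG from a vaccine, or with antibodies from an older infection, already meets the definition on Day 1. If those antibodies persist to Day 33, the participant is counted as positive in any arm and says nothing about the effect of EDP 235 on the antibody response to the present infection. Such participants still enter the CMH comparison.

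Two things are at stake. The reported proportion combines two sources of antibody and is hard to interpret. The difference between arms is also pulled towards zero by an amount that depends on the vaccination and infection history of the enrolled population, so a small difference could be misread as showing that treatment leaves the antibody response unchanged.

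**Working it through.** The SAP gives no sample size, baseline seropositivity, vaccination share or expected Day 33 proportion for this endpoint in its visible text, so there is no planned figure to reproduce. The dilution is algebra. Its size rests on assumptions.

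**Inputs**
- From the SAP: any-one-positive rule (5.3, reused in 8.3.7); two-sided alpha 0.05 (3.1); equal allocation to the arms (2.1).
- Assumed: s, the share positive on Day 1 and still positive on Day 33, is 30% to 90% and equal in both arms.
- Assumed: Day 33 positivity among the rest is c = 0.90 on placebo and 0.60 on drug, a 30-point contrast.
- Assumed: 75 participants per arm.

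**Formulae**
- Day 33 proportion in an arm = s + (1 − s) × c.
- Difference between arms = (1 − s) × (0.90 − 0.60) = (1 − s) × 0.30.
- Power: exact binomial enumeration of a two-sided pooled z-test, as an unstratified stand-in for the CMH test.

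Example at s = 0.80: placebo 0.80 + 0.20 × 0.90 = 0.98; drug 0.80 + 0.20 × 0.60 = 0.92; difference 0.06.

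| s | Placebo | Drug | Difference (points) | Power, planned analysis |
|---|---|---|---|---|
| 30% | 0.93 | 0.72 | 21 | 0.95 |
| 50% | 0.95 | 0.80 | 15 | 0.83 |
| 80% | 0.98 | 0.92 | 6 | 0.40 |
| 90% | 0.99 | 0.96 | 3 | 0.18 |

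**Restricting to participants negative on every antibody.** The contrast returns to 30 points, but only 75 × (1 − s) per arm remain:
- s = 50%: 37.5, taken as 38 per arm, power 0.89 (planned analysis 0.83).
- s = 80%: 15 per arm, power 0.51 (planned 0.40).
- s = 90%: 7.5 per arm, power 0.18 with 7 or 0.25 with 8 (planned 0.18). A z-test is unreliable at this size.

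This restriction makes the estimate interpretable but adds little power.

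**Restricting to participants negative for anti-nucleocapsid only.** This set keeps vaccinated participants who are positive on anti-spike alone, so it cannot be smaller than the set above. Suppose any-antibody positivity is 90%, and the same 90% versus 60% conversion applies to anti-nucleocapsid:
- Day 1 anti-nucleocapsid positivity 50%: 75 × 0.50 = 37.5, taken as 38 per arm, power 0.89.
- Day 1 anti-nucleocapsid positivity 70%: 75 × 0.30 = 22.5, taken as 23 per arm, power 0.69.

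The planned analysis has power 0.18 at s = 90%. The gain depends on how far anti-nucleocapsid positivity lies below any-antibody positivity, which the SAP does not state.

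**The case against.** The strongest reply is that the dilution may be modest. At s = 30% or 50% the planned test keeps power of about 0.95 or 0.83 under the assumptions above. Dilution towards the null does not invalidate a randomized comparison, and Section 5.3 already summarises baseline serostatus by arm, so a reader can see how much there is. This stands. It limits the size of the point but does not remove the mixing of two antibody sources.

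A second reply is that the visible text does not state the purpose of the endpoint. The objectives and endpoints after the secondary ones are redacted, and so is much of Section 8.3, where antibody-specific or baseline-stratified analyses may exist. This also stands: the point concerns the comparison that Section 8.3.7 itself specifies and does not claim that no other serology analysis is planned.

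Two stronger readings are tempting, and the SAP supports neither:
- A reader might infer that the proportion must sit at its ceiling and cannot show a treatment effect. That needs a high s, and the SAP gives no seroprevalence or vaccination share from which to derive one.
- A reader might infer that the asymmetric rule, where one result suffices for positive and all are needed for negative, inflates the summarised proportion. Section 3 takes percentages over all participants in the treatment group within the analysis set, with a row for missing values where needed. A participant with incomplete results and no positive therefore stays in the denominator. Section 8.3.7 does not override this.

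**Conclusion.** The point holds in a limited form. Reusing the any-one-positive rule at Day 33, in an infected population that may carry older antibodies, mixes earlier immunity with the current response and multiplies any treatment contrast by (1 − s). That factor follows from the SAP's own definitions, provided s is similar across arms, as randomization should make it.

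The size is conditional. With 75 per arm and 90% versus 60% seroconversion, all assumed, the loss runs from slight (21 of 30 points kept at s = 30%) to severe (3 of 30 points at s = 90%). Whether the proportion is close to its ceiling cannot be settled from the SAP. The consequence is small, because the endpoint is in Section 8.3, outside the primary and secondary efficacy sets of Sections 8.1 and 8.2.

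**What to change.** In Section 8.3.7, make the comparison between arms anti-nucleocapsid seroconversion at Day 33 among participants who were anti-nucleocapsid negative on Day 1. The Day 1 sample is taken predose according to the schedule of procedures, so selecting on it preserves the randomized comparison. Because anti-nucleocapsid marks infection only if the vaccine received does not induce it, check the vaccine type recorded under Section 6.2 and state how recipients of vaccines that do induce it are handled.

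Keep the any-antibody Day 33 proportion as a descriptive summary by baseline serostatus.

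The cost is SAP wording. Section 5.3 already names anti-nucleocapsid, and Section 8.3.7 already uses Day 33 serology, so no new samples are needed. The downside is a smaller analysed set, which is tolerable for an endpoint at this level.

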9.2. Intensive PK Subset Subjects

A small subset of subjects will be enrolled into an intensive PK sampling group. Approximately 30 subjects will be enrolled in this subset (10 from each of EDP 235 [REDACTED] and [REDACTED]). These subjects will have PK collections on Day 1 at 1, 2, 4, and 8 hours postdose, Day 3 predose, and Day 5 at predose, and 1, 2, 4, 8 hours postdose. Time and date of collection will be recorded on the Plasma PK Sample Collection eCRF.

PK collections that have an actual sampling time that deviates from the predefined collection time windows will be flagged in the data listings.

For subjects included in the intensive PK subset Population, plasma concentration data for EDP 235 will be summarized using descriptive statistics as described above using the unique timepoints in the intensive PK subset. PK parameters (C_{max} , t_{max} , C_8 , AUC_{0-last} , AUC_{0-8}) will be summarized. Mean (+/-standard error) and individual PK concentration over time (Day 1 and Day 5 to 8-hours postdose and Day 3 predose) by treatment group will be plotted on linear and semi-log scale.

Individual concentration data and PK parameters will be presented in listings.

9.3. PK Analyses

For subjects included in the intensive PK subset Population, plasma PK parameters for EDP 235 will be estimated using non-compartmental methods with WinNonlin[®] using best fit regression. The PK parameters will be estimated from the concentration-time profiles, and AUCs will be calculated using linear up / log down method. In estimating the PK parameters, BQL values before the first quantifiable point will be set to zero, BQL values that occur after the first quantifiable point will be considered missing. Values that are embedded between BQLs, or

quantifiable values occurring after two or more BQLs, will be set to missing at the discretion of the pharmacokineticist. Actual sampling times, rather than scheduled sampling times, will be used in all computations involving sampling times, and samples collected outside the allowable window will be included in the PK analysis. If the actual time or dose time is missing, the scheduled time may be substituted in order to calculate the PK parameters. Descriptive statistics (number of subjects, mean, geometric mean, SD, %CV, %GCV, median, min, and max) will be used to summarize the calculated PK parameters by treatment group. For t_{max} , only median, min and max will be presented.

Table 2 Plasma PK Parameters for EDP 235 are shown as below.

Table 2

| Parameter | Description | SAS Programming Notes |
|------------------|--------------------------------------------------------------------------------------------------------------------------------------------------------------------------------------------|------------------------------|
| C_{max} | Maximum plasma concentration. Observed peak analyte concentration obtained directly from the experimental data without interpolation, expressed in concentration units | C_{max} from WNL |
| t_{max} | Time to maximum plasma concentration. First observed time to reach peak analyte concentration obtained directly from the experimental data without interpolation, expressed in time units. | t_{max} from WNL |
| C_8 | Plasma concentration at 8 hours postdose. | From SAS |
| AUC_{0-last} | The area under the plasma concentration-time curve, from time 0 to the last measurable nonzero concentration, as calculated by the linear up/log down method. | AUC_{0-last} from WNL |
| AUC_{0-8} | Area under the concentration-time curve from time 0 to 8 hours postdose. | AUC_{0-8} from WNL |

9.4. PK/PD Analyses

PK/PD will be presented as scatter plots of absolute values and percent change from baseline versus PK concentration on a linear and log scale figures as follows:

- SARS-CoV-2 RNA Viral Load and PK Predose on Day 5
- SARS-CoV-2 RNA Viral Load Change From Baseline and PK Predose on Day 5
- SARS-CoV-2 RNA Viral Load AUC Days 1-5 and PK Predose on Day 5
- SARS-CoV-2 RNA Viral Load AUC Days 1-14 and PK Predose on Day 5
- COVID-19 signs/symptom score using the COVID-19 Symptom Diary and PK Predose on Day 5
- COVID-19 signs/symptom score using the COVID-19 Symptom Diary Change from Baseline and PK Predose on Day 5.

[REDACTED]

11. Data Monitoring Committee

The DMC will review the safety data from this study throughout the study and all outputs will use the safety population . The DMC will be headed by a DMC Chair and will include one or more physicians with expertise in SARS-CoV-2, consisting of expert(s) independent from the Sponsor. Procedures for data review, including timing and potential outcomes, roles and responsibilities, and interactions with the Sponsor and PPD, will be governed by a separate DMC charter.

[REDACTED]

[REDACTED]

13. References

CDC. (2001). Data table of BMI-for-age charts. Updated August 23, 2001. Available at: https://www.cdc.gov/growthcharts/html_charts/bmiagerev.htm

CDC. (2021). SARS-CoV-2 variant classifications and definitions. Updated December 1, 2021. Available at <https://www.cdc.gov/coronavirus/2019-ncov/variants/variant-classifications.html>

United States Food and Drug Administration Guidance Document. International Conference on Harmonization E6 Good Clinical Practice. May 1996.

United States Food and Drug Administration Guidance Document. International Conference on Harmonization E3 Structure and Content of Clinical Study Reports. July 1996.

United States Food and Drug Administration Guidance Document. International Conference on Harmonization E9 Statistical Principles for Clinical Trials. September 1998.

14. Appendices

14.1.1. Schedule of Study Procedures

| Period | SCR | Treatment | | | | Follow-up ^a | | | | | | LT Follow-up | | Notes | | |
|----------------------------|----------------------|----------------|----|------------------|----|------------------------|------------------|------------------|------------------|------------------|------------------|------------------|------------------|------------------|-------|--------------------------------------------------------------------------------------------------------------------------------------------------------------------------------------------------------------------------------------------------------------------------------------------------------------------------------------------------------------------------------------------------------------------------------------------------------------------------------------------------------------------------------------------------------------------------------------------------------------|
| | | 1 ^c | 2 | 3 | 4 | 5 ^c | 6 to 8 | 9 | 10 to 13 | 14 | 15 to 32 | 33 | Wk 12 | | Wk 24 | |
| Day | -1 to 1 ^b | 1 ^c | 2 | 3 | 4 | 5 ^c | 6 to 8 | 9 | 10 to 13 | 14 | 15 to 32 | 33 | Wk 12 | Wk 24 | | |
| Visit Name | SCR | V1 | T1 | V2 | T2 | EOT | V3 | V4 | V5 | V6 | EOFU | V7 | V8 | EOS | | |
| Type of Visit | C | C | T | C/H ^f | T | C/H ^f | C/H ^f | C/H ^f | C/H ^f | C/H ^f | C/H ^f | C/H ^f | C/H ^f | C/H ^f | | |
| Eligibility | | | | | | | | | | | | | | | | |
| Informed consent form | X | | | | | | | | | | | | X* | | | Informed consent must be obtained before conducting any study specific assessments. *Participants who completed the study at the EOFU (Day 33) visit will be asked to participate in the long-term follow-up. If the participant agrees to participate, informed consent must be obtained for the long-term follow-up. Protocol Section 12.1.3 AEs, concomitant medications and therapies, and medically attended visits should be captured in the eCRF retrospectively for subjects who re-enter the study; data will be collected starting the next day after the participant completes the EOFU visit. |
| Inclusion/exclusion review | X | X | | | | | | | | | | | | | | Protocol Section 4.1 and Protocol Section 4.2 |
| SARS-CoV-2 diagnostic test | X | | | | | | | | | | | | | | | The SARS-CoV-2 diagnostic test should be a PCR or rapid antigen test approved for use in the country; PCR test is preferred. A test is required at Screening if a positive result from a SARS-CoV-2 diagnostic test performed as part of clinical care within 24 hours prior to randomization is not available. If an NP swab is collected for the SARS-CoV-2 diagnostic test, one swab from the left nostril will be collected. Protocol Section 8.1.1 Protocol Section 8.1.2 |
| Demographics | X | | | | | | | | | | | | | | | Protocol Section 8.1.2 |

| Period | SCR | Treatment | | | | | | Follow-up ^a | | | | | | Notes |
|-----------------------------------------------|-----|-------------------------|----|------------------|----|------------------|-----------|------------------------|------------------|-------------|------------------|--------------------------|------------------|-----------------------------------------------------------------------------------------------------------------------------------------------------------------------------------------------------------------------------------------------------------------------------------------------------------------------------------------------------------------------------|
| | | 1 ^c Rand. | 2 | 3 | 4 | 5 ^e | 6 to 8 | 9 (±1d) | 10 to 13 | 14 (±1d) | 15 to 32 | 33 (±1d) ^e | Wk 12 | |
| Visit Name | SCR | V1 | T1 | V2 | T2 | EOT | V3 | V4 | V5 | V6 | EOFU | V7 | EOS | (C=clinic, T=telephone call or telehealth, H=home visit by trained health care provider) |
| Type of Visit | C | C | T | C/H ^f | T | C/H ^f | | C/H ^f | C/H ^f | | C/H ^f | C/H ^f | C/H ^f | |
| Medical, smoking and COVID-19 disease history | X | | | | | | | | | | | | | Protocol Section 8.1.2 |
| Prior medications and therapies | X | | | | | | | | | | | | | Section 8.1.3 |
| Physical examination (PE) | X | | | | | | | | | | | | | Full PE at Screening. Subsequent PEs performed at the discretion of investigator will be targeted to new signs and symptoms, including specific assessments for any changes from previous status. Protocol Section 8.1.4 |
| Weight, height, BMI | X | | | | | | | | | | | | | BMI=weight (kg)/height (m) ² . Protocol Section 8.1.5 |
| Vital signs | X | X ^d | X | X | X | X | | X | X | | X ^g | | | Vital signs include heart rate, respiratory rate, systolic and diastolic blood pressure, body temperature, and pulse oximetry. Vital signs will be measured after the participant has been supine for at least 5 minutes. If screening and randomization occur on different calendar days, vital signs should be repeated on D1 for baseline values. Protocol Section 8.3.1 |
| Pregnancy test | X | X ^d | | | | | | | | | X | | | For female participants of childbearing potential. Urine test will be performed at Screening. On D1 and Day 33 (EOFU), blood will be collected for serum pregnancy test to be performed by central laboratory. The screening urine pregnancy test results will be used to qualify participants at study entry. Protocol Section 8.1.6 |
| Randomization and Study Drug | | | | | | | | | | | | | | |

| Period | SCR | Treatment | | | | | | Follow-up ^a | | | | | | LT Follow-up | Notes | |
|----------------------------------------------------------------------|-----|----------------------|----------------|------------------|----|------------------|------------------|------------------------|------------------|------------------|------------------|------------------|-----------------------|------------------|-------|------------------------------------------------------------------------------------------------------------------------------------------------------------------------------------------------------------------------------------------------------------------------------------------------------------------------------------------------------------------------------------------------------------------------------------------------------------------------------------------------------------------------------------------------------------------------------------------------------------------------|
| | | -1 to 1 ^b | 1 ^c | 2 | 3 | 4 | 5 ^e | 6 to 8 | 9 (+1d) | 10 to 13 (+1d) | 14 (+1d) | 15 to 32 (+1d) | 33 (+1d) ^e | | | Wk 12 |
| Day | | 1 ^b | 1 ^c | 2 | 3 | 4 | 5 ^e | 6 to 8 | 9 (+1d) | 10 to 13 (+1d) | 14 (+1d) | 15 to 32 (+1d) | 33 (+1d) ^e | Wk 12 | Wk 24 | |
| Visit Name | SCR | V1 | T1 | V2 | T2 | EOT | V3 | V4 | V5 | V6 | EOFU | V7 | V8 | EOS | | |
| Type of Visit | C | C | T | C/H ^f | T | C/H ^f | C/H ^f | C/H ^f | C/H ^f | C/H ^f | C/H ^f | C/H ^f | C/H ^f | C/H ^f | | |
| Study Assessments | | | | | | | | | | | | | | | | |
| Clinical laboratory assessments (chemistry, hematology, coagulation) | | X ^{d*} | | X | | X | | X | | X | | X ^g | | | | *Blood samples for select laboratory assessments should be taken from all randomized subjects and sent to the local laboratory for these identified tests (noted with superscript “a” in Protocol Table 1), which should be assayed and reported in an expedited manner. Review of laboratory results is not required prior to randomization or dosing. In parallel, hematology, chemistry, and coagulation panels should be sent to the central laboratory with the other Day 1 samples. From D1 through D5, samples should be collected predose. See Protocol Section 1.4 for the list of laboratory assessments. |
| Follicle stimulating hormone | | X ^d | | | | | | | | | | | | | | Follicle-stimulating hormone should be tested in selected postmenopausal females. Protocol Section 8.1.6 |
| 12-lead ECG (resting) | | X ^d | | | | X | | | X | | | X ^g | | | | Protocol Section 8.3.2 |
| COVID-19 Symptom Diary | X | X ^d | X | X | X | X | X | X | X | X | X | X | X | | | The COVID-19 Symptom Diary will be completed by participants during Screening to determine eligibility and after randomization, predose on Day 1 as a baseline measurement. If Screening and Day 1 occur on the same calendar day, the Screening Diary entry will be used as the baseline measurement and a separate Day 1 Diary will not be collected. In addition, the diary will be completed once daily at the same time each day ±2 hours. Protocol Section 8.2.2 |
| Global Impression Questions | | X ^d | X | X | X | X | X | X | X | X | X | X | X | X ^h | | Global impression questions include Return to Usual Health, Return to Usual Activities, PGI-C and PGI-S questions, which will be answered every day from D 1 to D33 after the COVID-19 |

| Period | SCR | Treatment | | Follow-up ^a | | | | | | | | LT Follow-up | Notes | | |
|---------------------------------------------------------------------------|-----|-------------------------|--------------------------------------------------------------------------------|------------------------|----|------------------|------------------|------------------|-------------------|------------------|--------------------------------|------------------|------------------|------------------|------------------------------------------------------------------------------------------------------------------------------------------------------------------------------------------------------|
| | | 1 ^c Rand. | 2 | 3 | 4 | 5 ^e | 6 to 8 | 9 (±1d) | 10 to 13 (±1d) | 14 (±1d) | 15 to 32 (±1d) ^e | | | 33 (±7d) | Wk 12 (±7d) |
| Visit Name | SCR | V1 | T1 | V2 | T2 | EOT | V3 | V4 | V5 | V6 | EOFU | V7 | V8 | EOS | |
| Type of Visit | C | C | T | C/H ^f | T | C/H ^f | C/H ^f | C/H ^f | C/H ^f | C/H ^f | C/H ^f | C/H ^f | C/H ^f | C/H ^f | |
| | | | | | | | | | | | | | | | |
| EQ-5D-5L | | X ^d | | | | X | | | X | | X | | | X ^h | |
| NP swabs collection | | X ^d | | X | | X | | X | X | | X | X | | X | |
| SARS-CoV-2 serology sample collection | | X ^d | | | | | | | | | X | | | | |
| [REDACTED] | | | | | | | | | | | | | | | |
| Study staff review of COVID-19 Symptom Diary and other PRO questionnaires | | | Continuous from baseline through Day 33 | | | | | | | | | | | | Protocol Section 8.1.7 |
| Assess ICU admissions, hospitalizations, and medically attended visits | | | Continuous from randomization through end of study participation | | | | | | | | | | | | Medically attended visits include any unscheduled interactions with healthcare professionals other than study staff or designees that are not for routine health maintenance. Protocol Section 8.2.3 |
| Adverse events | | | Continuous from signing of ICF through end of study participation ⁱ | | | | | | | | | | | | Protocol Section 8.4 |
| Concomitant medications and therapies | | | Continuous from signing of ICF through end of study participation | | | | | | | | | | | | Concomitant medications and therapies will include the use of supplemental oxygen, increased |

| Period | SCR | Treatment | | Follow-up ^a | | | | | | LT Follow-up | | Notes | | |
|-----------------------------|----------------------|----------------|----|------------------------|----|------------------|------------------|------------------|------------------|------------------|------------------|------------------|------------------|------------------|
| | | 1 ^c | 2 | 3 | 4 | 5 ^e | 6 to 8 | 9 | 10 to 13 | 14 | 15 to 32 | | 33 | Wk 12 |
| Day | -1 to 1 ^b | 1 ^c | 2 | 3 | 4 | 5 ^e | 6 to 8 | 9 | 10 to 13 | 14 | 15 to 32 | 33 | Wk 12 | Wk 24 |
| Visit Name | SCR | V1 | T1 | V2 | T2 | EOT | V3 | V4 | V5 | V6 | EOFU | V7 | V8 | EOS |
| Type of Visit | C | C | T | C/H ^f | T | C/H ^f | C/H ^f | C/H ^f | C/H ^f | C/H ^f | C/H ^f | C/H ^f | C/H ^f | C/H ^f |
| PK sample collection | | X ⁺ | | X | | X ⁺⁺ | | | | | | X* | | |
| | | | | | | | | | | | | | | |

(C=clinic, T=telephone call or telehealth, H=home visit by trained health care provider)
use per PI judgment and mechanical ventilation.
Protocol Section 8.1.3

On D1, collect one postdose plasma PK sample at least 1 hr after dosing or right before the participant leaves the site, whichever is later. On D3 and D5, collect one plasma PK sample predose at the same approximate time as the NP swab collection. If the participant takes the study drug before the study site visit, a PK sample should be taken at the same approximate time as the NP swab collection.
+ On D1 and D5, intensive PK sampling will be conducted in a subset of participants. Additional PK samples will be drawn at 1, 2, 4, and 8 hours postdose. See Protocol Table 4 for time windows for intensive PK sampling.
* If a participant discontinues treatment before D5 and remains in the study, a PK sample should be taken at the approximate time as the NP swab at the EOT Visit. If the subject discontinues treatment before D5 and does NOT remain in the study, a PK sample should be taken at the approximate time as the NP swab at the EOFU visit (Protocol Section 8.5).

Abbreviations: BMI=body mass index; D=day; ECG=electrocardiogram; EOFU=end of follow-up; EOS=end-of-study; EOT=end-of-treatment; ICF=informed consent form; LT=long-term follow-up; NP=nasopharyngeal; PGI-C: Patient Global Impression of Change; PGI-S: Patient Global Impression of Severity; PK=pharmacokinetic; SARS-CoV-2=severe acute respiratory syndrome coronavirus 2; SCR=screening

^a During the Follow-up period (Day 6 through Day 33), if the participant has symptom recurrence or symptom worsening, an unscheduled visit should be done within 2 days of patient reported symptom recurrence or worsening. At the unscheduled visit, NP swabs will be collected in addition to clinical assessments deemed necessary by the Investigator.

^b Screening assessments should occur within 24 hours of randomization.

- c. D1 assessments are to be done only in randomized participants. Randomization, predose baseline measurements, and dosing must occur on the same calendar date.
- d. These assessments should be done predose as baseline measurements
- e. Participants who discontinue treatment before completing 5 days of dosing should return to the study site within 24 hours of their last dose to complete EOT procedures and proceed to complete all follow up assessments 4, 9 and 28 days (EOFU visit) after their last dose of study drug. Participants who discontinue the study before Day 33 (EOFU) should return to the study site within 24 hours and no more than 48 hours later to complete the EOFU procedures.
- f. Visits may be completed at the study site or by study site personnel via a home visit, if feasible.
- g. These assessments are only required for participants who discontinued the study before Day 5 (ie, do not have an EOT visit before discontinuing the study) or participants who discontinued the study after Day 5 and before Day 14. These participants should have an EOFU visit with additional assessments as indicated
- h. For the Week 12 and Week 24 assessments, paper questionnaires may be used for the Global Impression Questions and EQ-5D-5L and transcribed into the eCRF.
- i. At Week 12 and Week 24, study staff will contact each participant to ask if they have COVID-19 signs and symptoms and record that information into the AE eCRF.

